
SECONDARY ENDPOINTS
	
 1. Volume of blood transfusion within 24 hours of admission for patients with severe TBI (GCS \leq8 and evidence of brain injury on imaging) and for entire cohort of patients. 2. Thromboelastography parameters including maximum amplitude, reaction time, alpha angle, fibrinolysis, and platelet function at 3 and 6 hours of resuscitation, after every 6 units of whole blood equivalent (WB or PRBCs), at the time of completion of resuscitation (time of last unit of blood product given), and on ICU days 1, 3 and 5. 3. 30-day mortality; 4. Duration of need for renal replacement therapy, mechanical ventilation, ICU admission, and hospital stay; 5. Number of units of blood products transfused by component/product during first 24 hours of admission and total for hospitalization; 6. Complications which include 30-day mortality, clinical coagulopathy, infection, venous thromboembolism, cerebrovascular accident, acute coronary syndrome, transfusion-related lung injury, transfusion-associated cardiac overload; 7. Hemolysis as measured by haptoglobin, bilirubin, lactate dehydrogenase, and direct antiglobulin 8. Wastage of blood units

SAFETY EVALUATIONS
	
Complications which include death, clinical coagulopathy, infection, venous thromboembolism, cerebrovascular accident, acute coronary syndrome, transfusion-related lung injury, transfusion-associated cardiac overload;
 
Hemolysis as measured by haptoglobin, bilirubin, lactate

	dehydrogenase, and direct antiglobulin.
PLANNED INTERIM ANALYSES	When approximately 50% of patients have been enrolled in the study, an interim analysis for safety will be conducted by the statistician and independent medical monitor. Serious adverse events will be monitored by the medical monitor on an ongoing basis throughout the study.

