5 CRITERIA FOR EVALUATION

5.1 Primary Efficacy Endpoint

The primary objective is to assess the clinical efficacy of whole blood compared to component therapy for trauma patients requiring massive transfusion. Primary analysis will compare volume of blood transfusion within 24 hours of admission for patients without severe TBI (defined as GCS \leq 8 and imaging evidence of brain injury) for patients who received WB versus component therapy for initial resuscitation.

Secondary Efficacy Endpoints

The secondary objectives will evaluate the effect on survival; the development of multiple complications related to survival; and wastage data. The full list of secondary endpoints is as follows:

1. Volume of blood transfusion within 24 hours of admission for patients with severe TBI (GCS \leq 8 and imaging evidence of brain injury) and for entire cohort of patients.
2. Thromboelastography parameters including maximum amplitude, reaction time, alpha angle, fibrinolysis, and platelet function at 3 and 6 hours of resuscitation, after every 6 units of whole blood equivalent (WB or PRBCs) given, at the time of completion of resuscitation (time of last unit of blood product given), and on ICU days 1, 3 and 5.
3. 30-day mortality;

PI: [name]

4. Duration of need for renal replacement therapy, mechanical ventilation, ICU admission, and hospital stay;
5. Number of units of blood products transfused by component/product during first 24 hours of admission and total hospitalization;
6. Complications which include clinical coagulopathy, infection, venous thromboembolism, cerebrovascular accident, acute coronary syndrome, transfusion-related lung injury, transfusion-associated cardiac overload during total hospitalization;
7. Hemolysis as measured by haptoglobin, bilirubin, lactate dehydrogenase, and direct antiglobulin on ICU day 1;
8. Wastage of blood units

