- The incidence of adverse events will be evaluated including: death, clinical coagulopathy, hemolysis, infection, venous thromboembolism, cerebrovascular accident, acute coronary syndrome, transfusion-related lung injury, transfusion-associated cardiac overload.
- The occurrence of any whole blood transfusion given to patients other than adult male trauma patients will also be recorded
- In addition to ongoing monitoring and final analysis, an interim safety analysis when approximately 50% of patients have been enrolled will determine if there is a difference in adverse events as defined above between groups.
- The interim analysis will be performed by the independent medical monitor. The independent medical monitor, [name], is an emergency medicine physician with extensive experience in clinical investigation and has no relation to the study other than to monitor safety. The independent medical monitor has the authority to stop the study if safety concerns arise, including but not limited to evidence for the pre-specified stopping criteria (see Section 12.5, Stopping Criteria). [name] is also independent of the Blood and Blood Derivatives Committee.

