10 EVALUATIONS BY VISIT

10.1 Visit 1 (Days 1-365)

Hospital Stay visit: typically 1-14 days, but can be as long as one year.

1. Assign the patient a unique study number. This number is planned to be listed on a bracelet in a packet present in the ED. The bracelet will be placed on the patient's wrist during initial admission procedures to identify the patient as a participant in the study.
2. All demographic data, past medical history, and concurrent medications are recorded by hospital staff as part of standard admission procedures. This information will be reviewed by study personnel during analysis.
3. Physical examination, vital signs, and standard clinical labs are performed and recorded by hospital staff.
4. Additional blood samples will be collected for TEG/platelet mapping and CAT (one 4 mL sodium citrate and one 4 mL heparinized tube per draw). This will be performed at the following time points: on admission, after each 6 units of whole blood equivalent (WB or PRBCs) transfused, at 3 and 6 hours of resuscitation, at the time of hemostasis determined by the trauma surgeon, and on ICU days 1,3 and 5.
5. Standard clinical labs including complete blood counts (white blood cell count, hemoglobin, hematocrit, and platelet count), blood chemistries, and standard coagulation labs (prothrombin time, international normalized ratio, partial thromboplastin time) will be performed at least daily as standard of care. This data will also be collected as part of the study. Of note, serial platelet counts obtained

PI: [name]

as standard of care will be monitored no less frequently than daily at noon (see also Schedule of Events).

6. In addition to standard clinical labs, hemolysis labs will be performed as listed above on ICU day 1 which will be billed to the study.
7. Follow up by chart review will continue for the duration of the hospital stay (typically roughly 14 days but can be up to one year).
8. Chart review during the hospital stay will collect the following data:

Data collected on initial 24 hours of hospital stay:

Medical record number

Date of birth /age

Sex

Race

Weight

Height

Injury date/time

Arrival date/time

Emergency Department exit date/time

Operating room arrival time

Tier (defines levels of critical condition for trauma patients)

Injury description

Mechanism of injury

Injury Severity Score

Glasgow Coma Scale and vitals

Intubation status and location of intubation

Whether patient received cardiopulmonary resuscitation

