12.5 Stopping Criteria

Pre-specified stopping criteria are as follows:

1. Hemolytic transfusion reaction: Defined as a clinical syndrome within 24 hours of blood transfusion including one or more symptoms (back pain, shortness of breath, hematuria, chills, dizziness, fever, urticaria) with clinical or laboratory evidence of hemolysis (hematuria, decreased haptoglobin, increased lactate dehydrogenase or bilirubin, or positive direct antigen test). Requires immediate cessation of ongoing blood transfusion and reporting as SAE. As this is an unexpected and serious event, any hemolytic transfusion reaction following the administration of whole blood will prompt temporary cessation of the study while the event is evaluated. If the event indeed occurred after administration of low titer group O-positive whole blood, the study will be stopped.

2. Additionally, interim analysis will seek evidence for increased incidence of clinical coagulopathy, increased transfusion requirements, and increased incidence of complications as defined above in Secondary Endpoints, or increased mortality, all of which will prompt stopping the study.

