15.4 Analysis of Secondary Endpoints

Continuous variables and categorical variables will be analyzed as described above (section 15.3). Mixed effects linear regression models will be used to evaluate coagulopathy over time and to adjust for confounding variables.

To analyze coagulopathy over time we will use a mixed effects linear regression model. A mixed effects linear regression model will also be used to adjust for confounding variables such as sex, age, comorbidities, severity of injury, and physiologic parameters of shock including pH and temperature, and use of a rapid transfuser (which more effectively warms blood).

Quarterly safety monitoring will compare categorical variables including mortality and development of complications (duration of need for renal replacement therapy,

PI: [name]

mechanical ventilation, ICU admission, and hospital stay; clinical coagulopathy, infection, venous thromboembolism, cerebrovascular accident, acute coronary syndrome, transfusion-related lung injury, transfusion-associated cardiac overload; transfusion reactions including clinical transfusion reactions and rates of hemolysis as measured by haptoglobin, bilirubin, lactate dehydrogenase, and direct antiglobulin). Categorical variables will be compared using the chi-squared test.

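### Complications are counted to death or discharge without regard to early death, so a difference in early survival can distort the comparison that Section 12.5 uses for stopping

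*Protocol*

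**What the plan says.** Four parts of the protocol bear on this.

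- **Window and content.** Section 5.1, secondary endpoint 6, lists clinical coagulopathy, infection, venous thromboembolism, stroke, acute coronary syndrome, "transfusion-related lung injury, transfusion-associated cardiac overload during total hospitalization". Death is not in that list; 30-day mortality is item 3. Section 10.1 states: "Follow up by chart review will continue for the duration of the hospital stay". Observation for complications therefore ends at death or discharge.
- **Measure.** Section 15.4: "Quarterly safety monitoring will compare categorical variables including mortality and development of complications", and "Categorical variables will be compared using the chi-squared test".
- **Consequence.** Section 12.5, item 2, has the interim analysis look for "increased incidence of complications as defined above in Secondary Endpoints, or increased mortality, all of which will prompt stopping the study". It sets no threshold and does not weigh complications against mortality.
- **A second definition.** Item 6 of the synopsis secondary endpoints reads "Complications which include 30-day mortality, clinical coagulopathy, infection, venous thromboembolism, cerebrovascular accident" and so on, which puts mortality inside the complication list. Section 5.2, on what is compared for safety, says "The incidence of adverse events will be evaluated including: death, clinical coagulopathy, hemolysis, infection" and continues with the other events. It therefore has death, and also hemolysis, in the list.

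**The concern.** A proportion with an event by death or discharge depends on two things: the risk of the event, and how long patients live to be at risk. In a population whose mortality the protocol calls high (Section 9.1.7), with a product that it hopes may lower mortality (Section 2.1), the second cannot be taken as equal between arms.

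If whole blood keeps more patients alive through the first hours, more of them reach the days in which infection or thromboembolism can develop. Their proportion with a complication then rises with no change in risk. If whole blood worsens early survival, the proportion falls and real harm can be masked. Either error matters, because Section 12.5 makes a rise in complications a reason to stop in its own right.

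Section 12.5 also refers back to the Secondary Endpoints for its definition, and the protocol has two versions of that item.

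**Working it through.** **No planned figure to reproduce.** The protocol gives no early mortality, complication rate or stopping boundary, so every rate below is an assumption shown over a range. From the protocol come only the sizes: 49 per arm, and an interim at about half of 98 enrolled (Section 15.5), so roughly 24 per arm if accrual is balanced.

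**Model.** Let *d* be the proportion dying before a later complication could occur, and *q* the complication risk among early survivors, equal in both arms.

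- Proportion ever having a complication = (1 − *d*) × *q*
- Spurious excess for whole blood = *q* × (*d* control − *d* whole blood)
- Death or complication = *d* + (1 − *d*) × *q*

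**Spurious excess, control early death 30%**

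| Survivor risk *q* | Whole blood death 25% | 20% | 15% |
|---|---|---|---|
| 20% | +1 | +2 | +3 |
| 40% | +2 | +4 | +6 |
| 50% | +2.5 | +5 | +7.5 |

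(percentage points against whole blood)

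**One case in full: *q* = 40%, early death 30% v 15%**

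- Ever a complication: 0.70 × 0.40 = 28% control; 0.85 × 0.40 = 34% whole blood.
- Among early survivors: 40% in both arms.
- Death or complication: 30 + 28 = 58% control; 15 + 34 = 49% whole blood.

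Exact binomial probabilities for this case:

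| Quantity | Equal survival (30% v 30%) | 30% v 15% |
|---|---|---|
| Higher whole blood complication count, 24 per arm | 44% | 62% |
| Same, 49 per arm | 46% | 70% |
| Chi-squared nominally significant against whole blood, 24 per arm | 2.6% | 6.6% |
| Same, 49 per arm | 2.5% | 9.1% |
| Higher whole blood death-or-complication count, 24 per arm | 44% | 22% |

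**Reverse direction.** With early death 20% control and 30% whole blood, *q* = 40%: ever a complication is 0.80 × 0.40 = 32% control and 0.70 × 0.40 = 28% whole blood, so the arm with more deaths looks safer. Death or complication is 52% v 58%, which shows the harm.

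**What cancels it.** The proportions are equal when the whole blood survivor risk is lower by the ratio (1 − *d* control)/(1 − *d* whole blood): 0.70/0.85 = 0.82, 0.70/0.80 = 0.88 and 0.70/0.75 = 0.93 for whole blood early death of 15%, 20% and 25%.

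**Competing-risk summary.** With complete follow-up to the end of the window, the cumulative incidence of a complication with death as a competing event equals (1 − *d*) × *q*. That is again 28% v 34%, so this method does not remove the distortion. The composite does change the reading.

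**The case against.** **Early events.** Coagulopathy, transfusion-related lung injury and circulatory overload can occur within hours, so a patient who dies early may already have had one. The background section itself links coagulopathy to death from exsanguination. A reader might infer that every early death counts as complication-free; the documents do not support that. This stands, and it confines the point mainly to infection and venous thromboembolism, and to a lesser degree stroke and coronary events.

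**The effect is conditional.** A reader might infer that a survival benefit will show up as harm and stop the study. The protocol supports only a tendency. It gives no rates, the effect needs a real early survival difference, and a modest benefit among survivors offsets it. A numerically higher count is also not a significant test: in the worked case the interim chi-squared goes against whole blood in 6.6% of trials, not 62%. That too stands. But Section 12.5 names no test or threshold, so a numerical excess is not ruled out as a trigger.

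**Mortality is visible.** Section 5.2 lists death among the events compared at the interim, and Section 12.5 names mortality in the same sentence. Deaths are not hidden from the monitor. Still, the two are joined as alternative reasons to stop, and nothing says that one qualifies the other.

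**The synopsis may already fix it.** Listing 30-day mortality among complications could be read as a composite. The protocol never says that the items form one combined endpoint, and the synopsis also lists mortality separately. That an ever/never count is meant is likewise inferred, from the words for development and incidence and from the chi-squared test, but the protocol offers no other reading.

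**It belongs in the SAP.** Competing-risk detail normally would. The window, the test, the stopping trigger and the two lists, however, are set in the protocol.

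**Conclusion.** The point holds as a conditional distortion together with an inconsistency. The inconsistency needs no assumption: the item to which Section 12.5 refers includes 30-day mortality in the synopsis and excludes it in Section 5.1.

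The distortion applies to later complications. It is about 1 to 7.5 points against the better-surviving arm, given control early death of 30%, whole blood early death of 25% to 15%, and an equal survivor risk of 20% to 50%. It reverses if whole blood survival is worse. The documents do not show that such a survival difference will occur, nor that the study would be stopped because of it. They do show that the complication comparison, read alone, cannot separate a change in complication risk from a change in early survival. It should be corrected before the interim analysis.

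**What to change.** 1. Use one item 6 definition in the synopsis, Sections 5.1 and 5.2, and the reference in Section 12.5, and say whether death is part of it.
2. Add an in-hospital death-or-complication comparison truncated at day 30, next to the individual complication proportions. Event start dates (Section 9.1.7) and date of death (Section 10.1) are already collected.
3. State in Sections 12.5 and 15.5 that the interim review reads complications together with mortality through this composite.
4. Cumulative incidence with death as a competing event may be shown descriptively, but should not be presented as the remedy.

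Follow-up for complications after discharge is not needed, because the composite is confined to the hospital stay.

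The cost is protocol and SAP wording plus one extra analysis. The composite mixes death with less severe events, so its components must still be shown separately.

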5.2 Safety Evaluations

- Hemolysis will be measured by haptoglobin, bilirubin, lactate dehydrogenase, and direct antiglobulin tests on ICU day 1. Clinical surveillance for evidence of hemolysis will also be ongoing. The Blood and Blood Derivatives committee will review data for the first 10 patients to receive whole blood for evidence of hemolysis and thrombocytopenia. If the risks of these conditions are judged by the Committee to be equivalent to risks seen following treatment with similar amounts of component therapy, the Committee will allow an increase from up to 4 units to up to 5 units of whole blood to be transfused. After 10 patients have received whole blood under this protocol, the Committee will again evaluate for hemolysis and thrombocytopenia and increase to a maximum of 6 units of whole blood if risks are found to be equivalent to component therapy.
- Alternatively, should the safety of up to 4 units of whole blood be published before 10 patients have received whole blood, the Committee will allow an increase to a maximum of 5 units of whole blood. The Committee will assess the first 10 patients to receive whole blood under this protocol and if the risks of hemolysis and thrombocytopenia are judged by the Committee to be equivalent to risks seen following treatment with similar amounts of component therapy, the Committee will allow up to 6 units of whole blood to be transfused.
- The Blood and Blood Derivatives Committee at UCLA, also known as the Transfusion Committee, is composed of Transfusion Medicine faculty members. The Committee performs routine monthly monitoring of all transfusion-related safety

PI: [name]

data, including evidence of hemolysis and other transfusion reactions. In addition, the Committee has agreed to perform a separate evaluation of the cohort of patients receiving whole blood and compare this to equivalent patients receiving component therapy (as defined in the inclusion and exclusion criteria for the study), for the purposes of evaluating the safety of whole blood. [name], who are co-investigators in this study, are members of the Blood and Blood Derivatives Committee but will be recused from safety analysis related to this study to prevent conflict of interest. No other member of the Committee has a relationship to the study.

- The incidence of adverse events will be evaluated including: death, clinical coagulopathy, hemolysis, infection, venous thromboembolism, cerebrovascular accident, acute coronary syndrome, transfusion-related lung injury, transfusion-associated cardiac overload.
- The occurrence of any whole blood transfusion given to patients other than adult male trauma patients will also be recorded
- In addition to ongoing monitoring and final analysis, an interim safety analysis when approximately 50% of patients have been enrolled will determine if there is a difference in adverse events as defined above between groups.
- The interim analysis will be performed by the independent medical monitor. The independent medical monitor, [name], is an emergency medicine physician with extensive experience in clinical investigation and has no relation to the study other than to monitor safety. The independent medical monitor has the authority to stop the study if safety concerns arise, including but not limited to evidence for the pre-specified stopping criteria (see Section 12.5, Stopping Criteria). [name] is also independent of the Blood and Blood Derivatives Committee.

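### Thrombocytopenia gates the rise in the whole blood cap, but no endpoint, adverse event list, interim, quarterly or stopping comparison names it

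*Protocol*

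**What the plan says.** Protocol 4.1 and 5.2 tie higher whole blood exposure to two risks, hemolysis and thrombocytopenia. On the standard route in 5.2, "The Blood and Blood Derivatives committee will review data for the first 10 patients to receive whole blood for evidence of hemolysis and thrombocytopenia", and the cap goes from 4 to 5 units if both risks are judged equivalent to those after similar amounts of component therapy. The next step reads "After 10 patients have received whole blood under this protocol, the Committee will again evaluate for hemolysis and thrombocytopenia and increase to a maximum of" (the figure given there is 6 units), again subject to equivalence. A second route starts from outside evidence: "should the safety of up to 4 units of whole blood be published before 10 patients have received whole blood, the Committee will allow an" (here the rise is to 5 units). The first 10 whole blood patients are then assessed for both risks before 6 units are allowed.

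Section 5.2 also records that "the Committee has agreed to perform a separate evaluation of the cohort of patients receiving whole blood and compare this to equivalent patients receiving component" (that is, the component therapy group), for safety. It lists no variables and gives no timing for this.

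The adverse events to be compared are introduced as follows: "The incidence of adverse events will be evaluated including: death, clinical coagulopathy, hemolysis, infection, venous thromboembolism, cerebrovascular accident, acute coronary syndrome", then lung injury and cardiac overload. The interim compares these same events. The quarterly list in 15.4 includes "transfusion reactions including clinical transfusion reactions and rates of hemolysis as measured by haptoglobin" and the other hemolysis markers. Under 10.1, serial platelet counts obtained "as standard of care will be monitored no less frequently than daily at noon" are also study data.

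**The concern.** The protocol treats thrombocytopenia as serious enough to hold back a higher cap and singles out platelet counts for daily monitoring. It then assigns those counts to no named between-group comparison after the gate. Hemolysis, the other gating risk, is followed through to the end of the study.

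Every named thrombocytopenia review comes before the step to 6 units. The patients with the highest permitted exposure are therefore those for whom the protocol names no comparison on this risk. The study could report on the safety of up to 6 units with one of its two gating risks compared by arm only in a small early group, or compared later only if someone chose to do so.

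**Working it through.** The protocol states no figure on this point, so the check starts by setting its sections side by side.

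| Protocol section | Hemolysis | Thrombocytopenia or platelet count |
|---|---|---|
| 4.1 and 5.2, conditions for raising the cap | Named | Named |
| 5.1, secondary endpoints | Named (item 7) | Not named; item 2 has platelet function on thromboelastography, which is not a count |
| 5.2, listed adverse events, also used by the interim | Named | Not named |
| 12.5, stopping criteria | Named as hemolytic transfusion reaction (criterion 1) | Not named |
| 15.4, quarterly comparison | Named | Not named |
| 10.1 and Appendix I, data collected | Tests on ICU day 1 | Counts at least daily |

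The links between these lists matter. The interim in 5.2 uses the adverse events listed just before it. Criterion 2 in 12.5 uses the complications listed under the secondary endpoints. An item missing from the source list is therefore not named in the comparison built on it.

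**Share of patients outside named review.** Inputs: 49 whole blood patients planned (8.1) and reviews tied to 10 patients (5.2).

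- If both reviews concern the same first 10 patients: 49 − 10 = 39, and 39/49 = 79.6%.
- If the second review means a further 10 (an assumption): 49 − 20 = 29, and 29/49 = 59.2%.

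The text supports either reading, because both reviews on the standard route are tied to 10 patients and 5.2 does not say whether they are the same ones.

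**What reviews of this size can exclude.** With no events in n patients, the exact one-sided 95% upper bound on the risk is 1 − 0.05^(1/n).

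- n = 10: 1 − 0.05^(1/10) = 25.9%.
- n = 20: 1 − 0.05^(1/20) = 13.9%.

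Even a clean early review leaves a sizeable risk open, so it cannot stand in for comparison in later patients.

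**The case against.** A reader might infer that patients given 5 or 6 units are never compared on thrombocytopenia. The protocol does not support that. On both routes in 5.2 a thrombocytopenia review precedes the step to 6, and on either route it may include patients treated while 5 units were allowed. Whether it does is unclear. A reader might also infer that whole blood must be shown to be no worse before any rise. The standard in 5.2 is equivalence, and on the publication route the cap reaches 5 with no thrombocytopenia review in this study.

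Nor can it be said that no later comparison could include platelets. The Committee's cohort evaluation is not limited to the first 10 patients, and the same Committee applies the gate. Its monthly monitoring covers transfusion safety data in general. The adverse event list in 5.2 is open-ended, 11.1 lets an abnormal laboratory result count as an adverse event, and clinical coagulopathy, which is left undefined, might absorb some cases. The medical monitor may also stop the study for reasons beyond those listed. All of this stands, but it makes capture possible, not planned: none of these provisions names platelet count or thrombocytopenia.

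Finally, by-arm tabulation of a laboratory value is often left to the SAP, and section 15 announces one. That would answer the point if the protocol were silent. Here the protocol itself fixes the secondary endpoints as a complete list, sets out the events the interim compares, and itemises the quarterly variables. It carries one gating risk into them and not the other.

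**Conclusion.** The point holds as an inconsistency within the protocol. Thrombocytopenia is a condition for raising the cap but is named in no secondary endpoint, listed adverse event, interim, quarterly or stopping comparison. Patients treated once 6 units are allowed have no named comparison on it.

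The share of the whole blood group outside named review is 80% or 59%, depending on how the second review is read. Both figures assume that 49 whole blood patients are enrolled and that the Committee's unspecified evaluations are not counted as named review. If the cohort evaluation does include platelet counts, the gap is one of documentation only. The change is worth making because the risk is one the protocol itself treats as decisive and the data are already in hand.

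**What to change.** Reconcile the escalation text in 5.2 with the adverse event list in 5.2 and the quarterly list in 15.4:

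- Add lowest platelet count over days 0-5 and thrombocytopenia, with a definition fixed in advance, by arm, to the safety list in 5.2. The interim then picks them up through its reference to that list. Add them to 15.4 and to the final safety analysis as well.
- Show whole blood patients by the cap in force when they were treated, against component patients given similar amounts, which is the comparison the gate itself uses. Do not tabulate by raw units received: units follow bleeding severity, so a lower platelet count at higher units would be confounded.
- Report early deaths by arm beside the lowest count, because a patient who dies early has fewer days on which a low count can be observed.
- State whether the second review in 5.2 concerns the same 10 patients or a further 10, and whether the Committee's cohort evaluation includes platelet counts.

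No dose or stopping rule is proposed. The cost is one added safety variable, taken from counts already collected at least daily.

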8 STUDY TREATMENTS

8.1 Method of Assigning Patients to Treatment Groups

Treatment groups are not assigned as this is an observational study. Treatment is determined by the eligibility of the patient (male or female) and the availability of whole blood when the patient presents. Adult male patients meeting eligibility who have

PI: [name]

received or will receive whole blood for traumatic resuscitation will be enrolled in the whole blood group. Enrollment of 49 patients receiving whole blood is planned. Adult male patients meeting eligibility criteria who present when whole blood is not available will receive component therapy and will be enrolled in the component therapy group. Enrollment of 49 control (component therapy group) patients is planned. Female patients meeting eligibility criteria will also be included in the component therapy group (see Section 6.1, Study Population, for rationale).

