8.4.1 Dosage/Dosage Regimen

Adult male patients may receive up to 4 units of whole blood if needed during initial traumatic resuscitation in the initial phase of the study, and up to 6 units if deemed to be safe (see section 5.2, Safety Evaluations).

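### Section 5.2 lets the 5-to-6 unit review rest on the same ten whole blood patients as the 4-to-5 unit review, because it does not ask for further patients treated under the 5-unit limit

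*Protocol*

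**What the plan says.** Protocol Section 5.2 describes two routes from 4 to 6 units of whole blood.

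- **Main route, first step.** The Committee will "review data for the first 10 patients to receive whole blood for evidence of hemolysis and thrombocytopenia". If it judges the risks equivalent to those of similar amounts of component therapy, the limit rises from 4 to 5 units.
- **Main route, second step.** The next sentence reads: "After 10 patients have received whole blood under this protocol, the Committee will again evaluate for hemolysis and thrombocytopenia". If the risks are again found equivalent, the limit rises to 6 units.
- **Publication route.** This applies "should the safety of up to 4 units of whole blood be published before 10 patients have received whole blood". The limit then goes to 5 units on the published evidence, and the 6-unit decision has one internal review: "The Committee will assess the first 10 patients to receive whole blood under this protocol".

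Two other sections touch the escalation. Section 4.1 summarises it as moving to 6 units if the initial patients show no problem, and mentions no 5-unit stage. Section 8.4.1 allows "up to 6 units if deemed to be safe (see section 5.2, Safety Evaluations" and so sends the reader back to 5.2. Section 8.1 gives the size of the group: "Enrollment of 49 patients receiving whole blood is planned".

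**The concern.** A limit that moves from 4 to 5 and then to 6 units, with a review before each move, has a purpose only if experience at 5 units informs the decision on 6. The second-step sentence does not secure this. It repeats the count of ten without calling the patients additional, and without tying them to the period when 5 units were allowed. A Committee that applied the sentence as written could hold both reviews on the same ten patients, all treated when 4 units was the maximum. The second review would then contain no information that the first did not.

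What is at stake is the evidence behind a safety decision. For recent civilian use of this product, Section 1.2 cites a published study of up to 2 units and a personal communication about 4 units. The 5-unit stage is where the study would gather its own experience above 4 units before going further. Section 12.5 shows how seriously the hazard is taken: a hemolytic transfusion reaction confirmed after this product stops the study.

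**Working it through.** The protocol gives no figure to reproduce here. The check sets the sentences side by side and counts patients.

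**1. Is a second batch stated?**
- First review: the first ten whole blood patients.
- Second review: after ten patients have received whole blood under the protocol. No word means another ten, and no reference is made to the 5-unit limit.
- The qualifier about the protocol cannot easily be read as meaning the 5-unit stage. The publication-route bullet uses it for a count that plainly starts with the study's first whole blood patient ("The Committee will assess the first 10 patients to receive whole blood under this protocol").
- Sections 4.1 and 8.4.1 name no 5-unit group, so they do not settle the reading.

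**2. Patients treated under the 5-unit limit before the 6-unit review (main route)**

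Inputs: ten patients per review (Section 5.2) and 49 planned whole blood patients (Section 8.1).

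| Reading | Earliest 6-unit review | Under the 5-unit limit by then | Whole blood patients left |
|---|---|---|---|
| Literal: same ten | patient 10 | 10 − 10 = 0 | 49 − 10 = 39 (39/49 = 80%) |
| Second batch of ten | patient 10 + 10 = 20 | 20 − 10 = 10 | 49 − 20 = 29 (29/49 = 59%) |

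**3. Does another safeguard supply the missing data first?**
- Committee surveillance (5.2): "The Committee performs routine monthly monitoring of all transfusion-related safety" data. It continues throughout but sets no minimum experience at 5 units.
- Interim analysis (5.2): "an interim safety analysis when approximately 50% of patients have been enrolled". Half of 98 is 49 patients. If the two groups fill evenly, which is an assumption, that is about 24 or 25 whole blood patients, well after patient 10. It is not linked to the unit limit.
- Stopping rule (12.5): acts on a hemolytic reaction once it has happened, at any number of units.
- Quarterly safety monitoring (15.4): compares the groups on complications and is not linked to the unit limit.

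All of these protect patients. None requires data from the 5-unit stage before 6 units are allowed.

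**The case against.** The strongest reply is that the literal reading is the less sensible one. The text runs in order: review ten, raise to 5, then evaluate again. If both reviews fell on the same ten patients at the same moment, the 5-unit step and the repeat evaluation would have no function. This has force, and a second batch was probably meant. But the text does not say so, and the neighbouring bullet uses nearly the same phrase for a count from the start of the study. An escalation rule should not depend on which reading a Committee prefers.

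A second reply is that escalation is never automatic. Each step needs a judgement of equivalence with component therapy, the co-investigators on the Committee are recused, and the Committee may ask for more patients. All of this stands. It means that a cautious Committee could avoid the problem, though the protocol does not require it to.

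Three stronger readings are tempting, and the document does not support them.
- *That the publication route has the same defect.* It does not. That route is an explicit rule: published evidence replaces the first internal review, and ten study patients are reviewed before 6 units. The number of those ten treated under the 5-unit limit depends on when the publication appears, but nothing in the rule is misstated or contradicted. Changing it would be a preference.
- *That the gap can be expressed as an upper confidence limit on the event rate after no events in ten patients.* The Committee's criterion is a comparison with component therapy, not a zero-event rule. Such a limit would also describe patients for whom a fifth unit was allowed, not patients who received one.
- *That the sponsor meant to go to 6 units with no experience at 5.* The wording permits this but does not show it to be the intention.

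**Conclusion.** The point holds for the main route of Section 5.2. As written, the second review has the same count as the first and can be met by the same ten patients, so the minimum number treated under the 5-unit limit before 6 units open is 0. With a second batch it would be 10. No other provision in the protocol closes the gap.

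The size should be read with care. The contrast of 0 with 10 depends on the literal reading; if a second batch was intended, the defect is one of wording only. It also counts patients for whom a fifth unit was permitted. The protocol does not state how many would actually receive one. The primary endpoint and the sample size are not affected. This should be corrected because it concerns a safety step and costs little to put right.

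**What to change.** In the main route of Section 5.2, reword the second-step sentence so that the 6-unit review takes place after 10 additional patients have received whole blood under the 5-unit limit. Add that this review reports how many of those patients received a fifth unit. The equivalence judgement stays with the Committee, and the publication route stays as it is.

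The cost is one amended sentence and a possible delay. The 6-unit limit would open at whole blood patient 20 of 49 at the earliest instead of patient 10, so 29 instead of 39 patients could be treated under it. If a second batch was already intended, the change only makes that explicit and nothing is delayed.
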